**450 – Quadrivalent Influenza Vaccine**

---

Therefore an AE may be:

A new illness

The worsening of a concomitant illness

An effect of the vaccination, including the comparator

A combination of the above

All AEs include serious and non-serious AEs.

Surgical procedures are not AEs; they are the action taken to treat a medical condition. It is the condition leading to the action taken that is the AE (if it occurs during the trial period).

Pre-existing medical conditions are not to be reported as AEs. However, if a pre-existing condition worsens in frequency or intensity, or if in the assessment of the treating physician there is a change in its clinical significance, this change should be reported as an AE (exacerbation). This applies equally to recurring episodes of pre-existing conditions (e.g., asthma) if the frequency or intensity increases post-vaccination.

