***Serious Adverse Event (SAE):***

*Serious* and *severe* are not synonymous. The term *severe* is often used to describe the intensity of a specific event as corresponding to Grade 3. This is not the same as *serious* which is based on patient / event outcome or action criteria usually associated with events that pose a threat to a patient's life or functioning. Seriousness, not severity, serves as a guide for defining regulatory reporting obligations.

An SAE is any untoward medical occurrence that at any dose:

Results in death

Is life-threateninga

Requires inpatient hospitalization or prolongation of existing hospitalizationb

Results in persistent or significant disability / incapacityc

Is a congenital anomaly / birth defect

Is an important medical eventd

---

a The term "life-threatening" refers to an event in which the subject was at risk of death at the time of the event; it does not refer to an event which hypothetically might have caused death if it were more severe.

b All medical events leading to hospitalizations will be recorded and reported as SAEs, with the exception of: hospitalization planned before inclusion into the study or out-patient treatment with no hospitalization.

c "Persistent or significant disability or incapacity" means that there is a substantial disruption of a person's ability to carry out normal life functions.

d Medical and scientific judgment should be exercised in deciding whether expedited reporting is appropriate in other situations, such as important medical events that may not be immediately life-threatening or result in death or hospitalization but may jeopardize the health of the subject or may require intervention to prevent one of the

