***Solicited Reaction:***

A solicited reaction is an AE that is prelisted in the CRF. The assessment of these AEs post-vaccination is mandatory. A solicited reaction is defined by a combination of:

Symptom and

Onset post-vaccination

e.g., injection site swelling between D0 and D7 post-vaccination, or fever between D0 and D7.

A solicited reaction is therefore an AR observed and reported under the conditions (symptom and onset) prelisted (i.e., solicited) in the CRF and considered as related to vaccination.

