***Unsolicited AE / AR:***

An unsolicited AE is an observed AE that does not fulfill the conditions prelisted in the CRF in terms of diagnosis and / or onset post-vaccination, i.e., excluding solicited reactions, e.g., if fever between D0 and D7 is a solicited reaction (i.e., prelisted in the CRF), then a fever starting on D7 is a solicited reaction, whereas fever starting on D8 post-vaccination is an unsolicited AE.

An unsolicited non-serious AE is an unsolicited AE excluding SAEs.

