### 4.3 Derived Endpoints: Calculation Methods

Terms used in the clinical safety tables to describe the safety events are specified below.

AE: adverse event includes immediate, solicited, and unsolicited non-serious or serious event.

AR: adverse reaction corresponds to related AE.

Immediate AE/AR: unsolicited non-serious systemic AE ticked "immediate (within 30 minutes from the vaccination)" by the Investigator in the eCRF or electronic serious adverse event (eSAE) with time to onset within 30 minutes after vaccination with either dose 1 or dose 2.

SR: solicited reactions are events pre-listed in the eCRF, and which occurred during the solicited period (D0 through D7 after vaccination with either dose 1 or dose 2).

Unsolicited AE: AE recorded in the eCRF unsolicited form and eSAE, excluding SRs. Therefore, include immediate AEs.

Unsolicited non-serious injection site reactions are always recorded without relationship and analyzed as ARs.

Unsolicited AEs to be analyzed are AEs which occur between Visit 1 and Visit 2 (and between Visit 2 and Visit 3 for subjects requiring two doses). Unsolicited AEs occurring after the last visit - and which are not SAE - will be presented in separate listings.

SAE: unsolicited AE considered serious by the Investigator.

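### Section 4.3 limits SAEs in the safety tables to unsolicited AEs, which contradicts Section 4.2.1 for a serious solicited reaction

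*SAP*

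**What the plan says.** Section 4.3 opens with "Terms used in the clinical safety tables to describe the safety events are specified below", so its definitions govern the tables. Two of them matter here:

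- "Unsolicited AE: AE recorded in the eCRF unsolicited form and eSAE, excluding SRs"
- "SAE: unsolicited AE considered serious by the Investigator"

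The same section defines SRs by a prelisted term and onset in the solicited period, D0 through D7 after either dose. It does not define them by the form on which they are recorded.

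Section 4.2.1 defines the same concepts more broadly:

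- The SAE definition begins "An SAE is any untoward medical occurrence that at any dose" and then lists the seriousness criteria. Solicited status plays no part in them.
- Footnote b to the hospitalization criterion states "All medical events leading to hospitalizations will be recorded and reported as SAEs". Its only exceptions are a hospitalization planned before inclusion and out-patient treatment without hospitalization.
- "All AEs include serious and non-serious AEs"
- "A solicited reaction is an AE that is prelisted in the CRF"

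Section 4.2.2 sets the SAE endpoint from D0 to the end of the study. Section 4.2.3.2 gives an action-taken scale for solicited reactions whose code 4 is inpatient hospitalization.

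**The concern.** The two sections give opposite answers for one kind of event: a prelisted reaction that starts in the solicited window and meets a seriousness criterion. Under Section 4.2.1 it is an SAE. Under the definition that governs the tables it is not, and two programmers working from the same SAP could produce different SAE tables.

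The days affected are those just after each vaccination. If Section 4.3 is followed, the event stays in the solicited tables, which Section 5.1.2.2 describes by intensity, time of onset and number of days. In that section, seriousness and outcome are attached to SAEs only. Action taken is listed without derivation (Section 4.3.1.4.1). A hospitalization could therefore be visible in a listing and yet be missing from the SAE count.

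**Working it through.** The SAP states no figure that this point could change, so the check is a comparison of texts, followed by a count of the event types and days on which they disagree.

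**Step 1. Can a solicited reaction be an SAE under Section 4.3?** An SAE must be an unsolicited AE, and an unsolicited AE must not be an SR. So no SR can be an SAE.

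**Step 2. Can it be one under Section 4.2.1?** A solicited reaction is an AE, AEs may be serious, and a medical event leading to hospitalization is an SAE apart from the two exceptions. So it can.

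**Step 3. Does the SAP foresee such an event?** Yes. Code 4 on the action scale for solicited reactions is inpatient hospitalization.

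**Step 4. Worked example.** For fever, Section 4.2.1 puts the boundary as follows: "then a fever starting on D7 is a solicited reaction, whereas fever starting on D8 post-vaccination is an unsolicited AE". For a fever leading to hospitalization:

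| Onset | Class | SAE under 4.2.1 | SAE under 4.3 |
|---|---|---|---|
| D0 to D7 | solicited | yes | no |
| D8 or later | unsolicited | yes | yes, if the Investigator considers it serious |

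**Step 5. Which way does the rest of the SAP point?** Footnote b of Section 4.2.1 requires the hospitalized event to be recorded as an SAE. Section 4.3.1.3.1 asks only for a verbatim term before an SAE observation counts. Section 4.3.1.3.3 analyses all SAEs during the study and sets aside only those before vaccination. All three favour counting the event.

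**Step 6. Scope of the disagreement.**

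- Prelisted terms at 6 to 23 months (Tables 4.1 and 4.4): 3 + 6 = 9. From 2 years (Table 4.2 or 4.3, with Table 4.5): 3 + 5 = 8.
- Days after one injection: D0 to D7 is 8 days, D0 to D28 is 29 days, and 8/29 = 27.6%.
- Two-dose groups on the nominal schedule: D0 to D7 and D28 to D35 are 16 days, D0 to D56 is 57 days, and 16/57 = 28.1%.

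These percentages are shares of follow-up time. They are not estimates of how many SAEs would be lost.

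**Step 7. Illustration of one event.** Assume a group of 100 with exactly one SAE, and that it is a solicited reaction. The SAP's exact (Clopper-Pearson) method gives 1/100 = 1% (95% CI 0.03 to 5.45) if it is counted, and 0/100 = 0% (95% CI 0 to 3.62) if it is not. The single event is an assumption. The SAP gives no rate.

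**The case against.** The best defence reads Section 4.3 by form. Its unsolicited AE line refers to the unsolicited form and the eSAE, and Section 4.3.1.4.5 likewise separates solicited, unsolicited and SAE pages. On this view a hospitalized reaction is entered as an eSAE, Sections 4.3.1.3.1 and 4.3.1.3.3 count it, and the exclusion of SRs only keeps diary records out of the unsolicited counts. This is arguable and may be what was intended. It does not remove the contradiction, because the exclusion sits in the same sentence as the eSAE and SRs are defined by term and onset, not by form.

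Other parts of the defence stand and limit the consequence:

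- Sections 4.3.1.4.2 and 4.3.1.4.3 have seriousness and outcome summarized as they were collected, without restricting this to SAEs. A reader might infer from Section 5.1.2.2 that both are lost for a serious solicited reaction, but the SAP does not go that far.
- A reader might infer that the three early safety reviews would miss the event. They use line listings (Sections 3.1 and 5.4). The content list in Section 5.6, given for the adult review, includes solicited reactions as well as SAEs, so the event would be seen under either definition.
- A reader might take Grade 3 vomiting needing parenteral hydration (Table 4.4) as a second sign that serious solicited reactions are foreseen. Parenteral hydration is not a listed seriousness criterion, and footnote b exempts out-patient treatment. Only action code 4 supports the point.

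**Conclusion.** The contradiction is real. The SAE definition in Section 4.3 is wrong as written, because it is narrower than Section 4.2.1 and than the endpoint in Section 4.2.2.

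Its severity is minor. It affects descriptive counts only, since no hypothesis is tested. The event would still appear in the solicited tables and in listings, its frequency cannot be derived, and no stated figure changes. The conclusion assumes that the table programs follow Section 4.3 literally. If they follow the form-based reading, the tables come out right and only the text is at fault.

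A reader might infer that serious reactions would go unreported, or that more than a quarter of SAEs would be lost. The documents support neither. The recording and reporting duty in Section 4.2.1 is untouched, and 27.6% and 28.1% are window lengths divided by follow-up lengths.

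**What to change.** Make three wording changes in Section 4.3:

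1. Replace the SAE line with: *SAE: any AE, solicited or unsolicited, considered serious by the Investigator according to the criteria of Section 4.2.1, and any AESI.* This keeps the Investigator as the assessor and carries over the existing Section 4.2.1 rule on AESIs.
2. Amend the unsolicited AE line so that the exclusion of SRs does not remove eSAE records from the SAE tables. State there whether a serious solicited reaction also counts in the unsolicited AE tables.
3. Add a table footnote that a serious solicited reaction appears in both the solicited and the SAE tables.

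This needs no new data and no new analysis. The only downside is that some events are shown twice, which the footnote explains.

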#### 4.3.1 Safety

##### 4.3.1.1 Solicited Reactions

###### 4.3.1.1.1 Daily Intensity

All daily records for solicited reactions will be derived into daily intensity according to the following classification: None, Grade 1, Grade 2, Grade 3, or Missing.

For measurable injection site reactions for subjects aged 6 months to 11 years:

Grade 1:  $> 0$  to  $< 25$  mm

Grade 2:  $\geq 25$  to  $< 50$  mm

Grade 3:  $\geq 50$  mm

For measurable injection site reactions for subjects aged 12 years or older:

Grade 1:  $\geq 25$  to  $\leq 50$  mm

Grade 2:  $\geq 51$  to  $\leq 100$  mm

Grade 3:  $> 100$  mm

For Fever for subjects aged 6 to 23 months:

**450 – Quadrivalent Influenza Vaccine**

---

Grade 1:  $\geq 38.0^{\circ}\text{C}$  to  $\leq 38.5^{\circ}\text{C}$

Grade 2:  $> 38.5^{\circ}\text{C}$  to  $\leq 39.5^{\circ}\text{C}$

Grade 3:  $> 39.5^{\circ}\text{C}$

For Fever for subjects aged 2 years or older:

Grade 1:  $\geq 38.0^{\circ}\text{C}$  to  $\leq 38.4^{\circ}\text{C}$

Grade 2:  $\geq 38.5^{\circ}\text{C}$  to  $\leq 38.9^{\circ}\text{C}$

Grade 3:  $\geq 39.0^{\circ}\text{C}$

For the derivation of daily intensities the following sequential steps will be applied:

1. Solicited reactions (except Fever) with an investigator presence recorded as “No” and with all daily records missing then all daily intensities will be derived as None.
2. For non-measurable solicited reactions, daily intensities will correspond to daily records reported in the clinical database. For measurable solicited reactions the daily measurements reported in the clinical database will be converted based upon the intensity scales defined above as in the Section 9.2.3.2 of the protocol; this assumes a reaction that is too large to measure (NM, not measurable) is Grade 3. Note: The intensity could be considered “None” (not a reaction) in the analysis despite being considered a reaction by the investigator (e.g., swelling measurement  $> 0$  mm but  $< 25$  mm for subjects aged  $\geq 12$  years).

Missing measurements (for temperature or length) will not be replaced.

The maximum intensity during the solicited period will be computed without considering the ongoing period. If the solicited period is D0 through D7, for an ongoing event at D7, the intensities after D7 will not be considered.

Note: The maximum intensity on the ongoing period is derived from the record of the maximum intensity/measurement after the end of the solicited period following the rule described above.

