**4.3.1.1.3 Presence**

Presence is derived from the maximum overall intensity on the period considered:

- None: No presence
- Grade 1, Grade 2, or Grade 3: Presence
- Missing: Missing presence

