**450 – Quadrivalent Influenza Vaccine**

---

Subjects with at least one non-missing presence for a specific endpoint will be included in the analysis. Conversely, those without a non-missing presence will not be included in the analysis of the endpoint.

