**5.3.2 Safety**

Missing safety data will not be replaced. No search for outliers will be performed.

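### The SAP has no rule for an investigator 'Yes' with all daily records missing, so such solicited reactions leave the analysis while the matching 'No' stays in as a non-case

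*SAP*

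**What the plan says.** Section 4.3.1.1.1 derives daily intensities in sequential steps.

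- **Step 1** covers every solicited reaction apart from fever. It applies where the investigator answered 'No' and nothing was recorded on any day; its wording is "and with all daily records missing then all daily intensities will be derived as None".
- **Step 2** covers everything else. For non-measurable reactions, "daily intensities will correspond to daily records reported in the clinical database". Measurable reactions are graded from the recorded size, and "Missing measurements (for temperature or length) will not be replaced".

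Section 4.3.1.1.3 then states that "Presence is derived from the maximum overall intensity on the period considered". Its last category reads "Missing: Missing presence", and "those without a non-missing presence will not be included in the analysis of the endpoint".

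On missing data, section 5.3.2 opens with the general statement "Missing safety data will not be replaced". Its subsection 5.3.2.4 sends missing intensities of solicited reactions back to 4.3.1.1.1.

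None of these sections says what happens when the investigator's answer is 'Yes' and every daily record for that reaction is missing.

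**The concern.** The same source is accepted when it reports no reaction and ignored when it reports one. A 'No' without daily records stays in the denominator as a non-case. A 'Yes' without daily records disappears from the endpoint altogether.

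The situation can arise. Under section 4.2.3 the investigator asks at the visit about what is in the diary card and about other events since the previous visit. Step 1 itself presupposes that a presence answer can exist without daily records.

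Describing the safety profile in each age group is one of the trial's two objectives (section 2.2), and solicited reactions are a main part of it. The SAP treats incomplete information on other events differently:

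- An unsolicited non-serious event counts if it has a verbatim term and is not Grade 0 (4.3.1.2.1), and its missing intensity stays missing (5.3.2.4).
- Missing causality counts as related (5.3.2.2).
- Unsolicited events with missing onset are kept (4.3.1.2.4, 5.3.2.5).

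A solicited reaction that the investigator confirms, but that has no daily grade, is dropped.

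**Working it through.** **The SAP's own figures.** It gives no figure for this rule. The nearest is in section 5.5: 100 subjects give 0.95 probability of seeing an event of 3% frequency. Check: 1 - 0.97^100 = 0.952, which agrees. The exact intervals in Table 5.2 also reproduce; 45/95 gives 37.0 to 57.9, a width of 20.9 points.

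**Following the rules for one solicited reaction other than fever, with all daily records missing**

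| Investigator's answer | Daily intensity | Presence | Numerator | Denominator |
|---|---|---|---|---|
| 'No' | None (step 1) | No | 0 | 1 |
| 'Yes' | Missing (step 2) | Missing | 0 | 0 |
| Missing | Missing | Missing | 0 | 0 |

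The third row leaves the analysis whether or not a reaction occurred, so it does not come from the asymmetry.

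**Expected percentage where 'Yes' equals a case.** Let p be the true rate and q the share of 'Yes' answers with no daily record. Per subject, the numerator is p(1-q) and the denominator is 1-pq.

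- Reported rate = p(1-q)/(1-pq)
- Loss = p - p(1-q)/(1-pq) = pq(1-p)/(1-pq), which is positive for any q > 0 and 0 < p < 1

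The result does not depend on how many 'No' subjects have blank records, because all of them are kept.

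Both p and q are assumptions; the SAP gives neither. Reported rate in %:

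| p | q = 2% | q = 5% | q = 10% | q = 20% |
|---|---|---|---|---|
| 3% | 2.94 | 2.85 | 2.71 | 2.41 |
| 10% | 9.82 | 9.55 | 9.09 | 8.16 |
| 30% | 29.58 | 28.93 | 27.84 | 25.53 |
| 50% | 49.49 | 48.72 | 47.37 | 44.44 |
| 70% | 69.57 | 68.91 | 67.74 | 65.12 |
| Largest loss over all p (points) | 0.5 | 1.3 | 2.6 | 5.6 |

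In counts: of 100 subjects, 40 have the reaction. If 2 of those 40 have no daily record (q = 5%), the result is 38/98 = 38.8% instead of 40.0%.

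**Rare reactions.** The chance of counting at least one case of a 3% reaction in 100 subjects is 1 - (1 - 0.03(1-q))^100. It falls from 0.952 to 0.945 at q = 5% and to 0.935 at q = 10%. A single dropped 'Yes' can turn 1/100 into 0/99.

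**Redness and swelling from 12 years.** Here a size below 25 mm is graded None (4.3.1.1.1). Take 100 adults, 5 with a measured reaction of at least 25 mm and one 'Yes' without any measurement. The rule reports 5/99 = 5.05%. If the unmeasured reaction was below 25 mm, the correct figure is 5/100 = 5.0% and the rule overstates slightly. If it was 25 mm or more, the correct figure is 6/100 = 6.0% and the rule understates. The direction is not determined.

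**The case against.** **Step 1 may only decode a form.** It works per reaction, not per subject, and never mentions a missing diary. It fits a convention in which 'No' is entered and the daily fields are left blank. The fever exception fits this too, since temperature is recorded daily regardless (4.2.3.2). A reader might infer that the rule is about subjects who returned no diary; the SAP does not say so, and the form is not shown. This stands. It does not remove the gap, because the loss depends only on 'Yes' answers without records.

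**The asymmetry has a reason.** A 'No' fixes every day at None, whereas a 'Yes' fixes no day's grade, and section 4.3.1.1.7 deliberately puts measurement above the investigator's ongoing flag. That justifies leaving the grade missing. It does not justify discarding presence, except where size decides whether there is a reaction at all.

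**A contradiction with 5.3.2 might be inferred.** The general no-replacement statement seems to conflict with step 1. It does not: 5.3.2.4 routes solicited intensities to 4.3.1.1.1, so step 1 is a declared special rule.

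**A bias that is always downward might be inferred.** That fails for redness and swelling from 12 years. It also fails where the presence answer itself is missing, because the direction then depends on who is missing.

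**The effect is probably small.** The SAP gives no value for q. Its 5% drop-out figure in section 5.5 concerns evaluability for immunogenicity, not blank daily records. Diary completion is checked by call or home visit after each vaccination (Tables 3.1 and 3.2), and no hypothesis is tested. This stands as to size.

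**Conclusion.** The point holds in a limited form. As written, the rules keep an investigator's 'No' and lose the corresponding 'Yes' when all daily records for that reaction are missing. For all non-measurable solicited reactions, and for redness and swelling under 12 years (where any size above 0 mm is at least Grade 1), this biases the reported percentage downward. Fever is not affected by the asymmetry. For redness and swelling from 12 years the direction cannot be stated.

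The size rests on q, which is assumed. At 5% the loss is at most about 1.3 points, well inside an interval about 21 points wide. The larger losses in the table need a q of 10% or 20%, for which the SAP gives no basis. The calculation also takes the investigator's 'Yes' as correct. The case for acting is that the error is systematic, understates reactogenicity, weighs more for rare reactions and small age subgroups, and can be removed with an answer the derivation already uses.

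**What to change.** 1. Add to step 1 of 4.3.1.1.1: for every non-measurable solicited reaction, and for redness and swelling under 12 years, investigator presence 'Yes' with all daily records missing is analysed as presence 'Yes', with intensity, time of onset and number of days Missing. The subject is kept in numerator and denominator.
2. For redness and swelling at 12 years or older, leave such subjects out of the main percentage, report them in a separate row 'present, size unknown', and give the percentage with them counted as cases as a sensitivity figure (in the adult example above, 6/100 beside 5/99).
3. Adjust 4.3.1.1.3 so that presence can be 'Yes' with a missing grade, and add a Missing category to the displays in 4.3.1.1.4 and 4.3.1.1.5, which have none.
4. Leave 5.3.2 unchanged.

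The cost is a few lines of SAP text and derivation code before database lock, with no new data collection. The downside is that a few counted reactions will carry a missing grade.
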